17.3 Appendix 3: Declaration of Helsinki

WORLD MEDICAL ASSOCIATION DECLARATION OF HELSINKI

Ethical Principles for Medical Research Involving Human Subjects

Adopted by the 18th WMA General Assembly, Helsinki, Finland, June 1964, and amended by the:
29th WMA General Assembly, Tokyo, Japan, October 1975
35th WMA General Assembly, Venice, Italy, October 1983
41st WMA General Assembly, Hong Kong, September 1989
48th WMA General Assembly, Somerset West, Republic of South Africa, October 1996
52nd WMA General Assembly, Edinburgh, Scotland, October 2000
53th WMA General Assembly, Washington DC, USA, October 2002 (Note of Clarification added)
55th WMA General Assembly, Tokyo, Japan, October 2004 (Note of Clarification added)
59th WMA General Assembly, Seoul, Republic of Korea, October 2008
64th WMA General Assembly, Fortaleza, Brazil, October 2013

Preamble

1. The World Medical Association (WMA) has developed the Declaration of Helsinki as a statement of ethical principles for medical research involving human subjects, including research on identifiable human material and data.

The Declaration is intended to be read as a whole and each of its constituent paragraphs should be applied with consideration of all other relevant paragraphs.

2. Consistent with the mandate of the WMA, the Declaration is addressed primarily to physicians. The WMA encourages others who are involved in medical research involving human subjects to adopt these principles.

General Principles

3. The Declaration of Geneva of the WMA binds the physician with the words, “The health of my patient will be my first consideration,” and the International Code of Medical Ethics declares that, “A physician shall act in the patient's best interest when providing medical care.”

4. It is the duty of the physician to promote and safeguard the health, well-being and rights of patients, including those who are involved in medical research. The physician's knowledge and conscience are dedicated to the fulfilment of this duty.

5. Medical progress is based on research that ultimately must include studies involving human subjects.

6. The primary purpose of medical research involving human subjects is to understand the causes, development and effects of diseases and improve preventive, diagnostic and therapeutic interventions (methods, procedures and treatments). Even the best proven interventions must be evaluated continually through research for their safety, effectiveness, efficiency, accessibility and quality.

7. Medical research is subject to ethical standards that promote and ensure respect for all human subjects and protect their health and rights.
8. While the primary purpose of medical research is to generate new knowledge, this goal can never take precedence over the rights and interests of individual research subjects.
9. It is the duty of physicians who are involved in medical research to protect the life, health, dignity, integrity, right to self-determination, privacy, and confidentiality of personal information of research subjects. The responsibility for the protection of research subjects must always rest with the physician or other health care professionals and never with the research subjects, even though they have given consent.
10. Physicians must consider the ethical, legal and regulatory norms and standards for research involving human subjects in their own countries as well as applicable international norms and standards. No national or international ethical, legal or regulatory requirement should reduce or eliminate any of the protections for research subjects set forth in this Declaration.
11. Medical research should be conducted in a manner that minimises possible harm to the environment.
12. Medical research involving human subjects must be conducted only by individuals with the appropriate ethics and scientific education, training and qualifications. Research on patients or healthy volunteers requires the supervision of a competent and appropriately qualified physician or other health care professional.
13. Groups that are underrepresented in medical research should be provided appropriate access to participation in research.
14. Physicians who combine medical research with medical care should involve their patients in research only to the extent that this is justified by its potential preventive, diagnostic or therapeutic value and if the physician has good reason to believe that participation in the research study will not adversely affect the health of the patients who serve as research subjects.
15. Appropriate compensation and treatment for subjects who are harmed as a result of participating in research must be ensured.

Risks, Burdens and Benefits

16. In medical practice and in medical research, most interventions involve risks and burdens.

Medical research involving human subjects may only be conducted if the importance of the objective outweighs the risks and burdens to the research subjects.

17. All medical research involving human subjects must be preceded by careful assessment of predictable risks and burdens to the individuals and groups involved in the research in comparison with foreseeable benefits to them and to other individuals or groups affected by the condition under investigation.

Measures to minimise the risks must be implemented. The risks must be continuously monitored, assessed and documented by the researcher.

18. Physicians may not be involved in a research study involving human subjects unless they are confident that the risks have been adequately assessed and can be satisfactorily managed.

When the risks are found to outweigh the potential benefits or when there is conclusive proof of definitive outcomes, physicians must assess whether to continue, modify or immediately stop the study.

Vulnerable Groups and Individuals

19. Some groups and individuals are particularly vulnerable and may have an increased likelihood of being wronged or of incurring additional harm.

All vulnerable groups and individuals should receive specifically considered protection.

20. Medical research with a vulnerable group is only justified if the research is responsive to the health needs or priorities of this group and the research cannot be carried out in a non-vulnerable group. In addition, this group should stand to benefit from the knowledge, practices or interventions that result from the research.

Scientific Requirements and Research Protocols

21. Medical research involving human subjects must conform to generally accepted scientific principles, be based on a thorough knowledge of the scientific literature, other relevant sources of information, and adequate laboratory and, as appropriate, animal experimentation. The welfare of animals used for research must be respected.

22. The design and performance of each research study involving human subjects must be clearly described and justified in a research protocol.

The protocol should contain a statement of the ethical considerations involved and should indicate how the principles in this Declaration have been addressed. The protocol should include information regarding funding, sponsors, institutional affiliations, potential conflicts of interest, incentives for subjects and information regarding provisions for treating and/or compensating subjects who are harmed as a consequence of participation in the research study.

In clinical trials, the protocol must also describe appropriate arrangements for post-trial provisions.

Research Ethics Committees

23. The research protocol must be submitted for consideration, comment, guidance and approval to the concerned research ethics committee before the study begins. This committee must be transparent in its functioning, must be independent of the researcher, the sponsor and any other undue influence and must be duly qualified. It must take into consideration the laws and regulations of the country or countries in which the research is to be performed as well as applicable international norms and standards but these must not be allowed to reduce or eliminate any of the protections for research subjects set forth in this Declaration.

The committee must have the right to monitor ongoing studies. The researcher must provide monitoring information to the committee, especially information about any serious adverse events. No amendment to the protocol may be made without consideration and approval by

the committee. After the end of the study, the researchers must submit a final report to the committee containing a summary of the study's findings and conclusions.

Privacy and Confidentiality

24. Every precaution must be taken to protect the privacy of research subjects and the confidentiality of their personal information.

Informed Consent

25. Participation by individuals capable of giving informed consent as subjects in medical research must be voluntary. Although it may be appropriate to consult family members or community leaders, no individual capable of giving informed consent may be enrolled in a research study unless he or she freely agrees.

26. In medical research involving human subjects capable of giving informed consent, each potential subject must be adequately informed of the aims, methods, sources of funding, any possible conflicts of interest, institutional affiliations of the researcher, the anticipated benefits and potential risks of the study and the discomfort it may entail, post-study provisions and any other relevant aspects of the study. The potential subject must be informed of the right to refuse to participate in the study or to withdraw consent to participate at any time without reprisal. Special attention should be given to the specific information needs of individual potential subjects as well as to the methods used to deliver the information.

After ensuring that the potential subject has understood the information, the physician or another appropriately qualified individual must then seek the potential subject's freely-given informed consent, preferably in writing. If the consent cannot be expressed in writing, the non-written consent must be formally documented and witnessed.

All medical research subjects should be given the option of being informed about the general outcome and results of the study.

27. When seeking informed consent for participation in a research study the physician must be particularly cautious if the potential subject is in a dependent relationship with the physician or may consent under duress. In such situations the informed consent must be sought by an appropriately qualified individual who is completely independent of this relationship.

28. For a potential research subject who is incapable of giving informed consent, the physician must seek informed consent from the legally authorised representative. These individuals must not be included in a research study that has no likelihood of benefit for them unless it is intended to promote the health of the group represented by the potential subject, the research cannot instead be performed with persons capable of providing informed consent, and the research entails only minimal risk and minimal burden.

29. When a potential research subject who is deemed incapable of giving informed consent is able to give assent to decisions about participation in research, the physician must seek that assent in addition to the consent of the legally authorised representative. The potential subject's dissent should be respected.

30. Research involving subjects who are physically or mentally incapable of giving consent, for example, unconscious patients, may be done only if the physical or mental condition that prevents giving informed consent is a necessary characteristic of the research group. In such circumstances the physician must seek informed consent from the legally authorised representative. If no such representative is available and if the research cannot be delayed, the study may proceed without informed consent provided that the specific reasons for involving subjects with a condition that renders them unable to give informed consent have been stated in the research protocol and the study has been approved by a research ethics committee. Consent to remain in the research must be obtained as soon as possible from the subject or a legally authorised representative.

31. The physician must fully inform the patient which aspects of their care are related to the research. The refusal of a patient to participate in a study or the patient's decision to withdraw from the study must never adversely affect the patient-physician relationship.

32. For medical research using identifiable human material or data, such as research on material or data contained in biobanks or similar repositories, physicians must seek informed consent for its collection, storage and/or reuse. There may be exceptional situations where consent would be impossible or impracticable to obtain for such research. In such situations the research may be done only after consideration and approval of a research ethics committee.

Use of Placebo

33. The benefits, risks, burdens and effectiveness of a new intervention must be tested against those of the best proven intervention(s), except in the following circumstances:

Where no proven intervention exists, the use of placebo, or no intervention, is acceptable; or

Where for compelling and scientifically sound methodological reasons the use of any intervention less effective than the best proven one, the use of placebo, or no intervention is necessary to determine the efficacy or safety of an intervention and the patients who receive any intervention less effective than the best proven one, placebo, or no intervention will not be subject to additional risks of serious or irreversible harm as a result of not receiving the best proven intervention.

Extreme care must be taken to avoid abuse of this option.

Post-Trial Provisions

34. In advance of a clinical trial, sponsors, researchers and host country governments should make provisions for post-trial access for all participants who still need an intervention identified as beneficial in the trial. This information must also be disclosed to participants during the informed consent process.

Research Registration and Publication and Dissemination of Results

35. Every research study involving human subjects must be registered in a publicly accessible database before recruitment of the first subject.

36. Researchers, authors, sponsors, editors and publishers all have ethical obligations with regard to the publication and dissemination of the results of research. Researchers have a duty to make publicly available the results of their research on human subjects and are accountable for the completeness and accuracy of their reports. All parties should adhere to accepted guidelines for ethical reporting. Negative and inconclusive as well as positive results must be published or otherwise made publicly available. Sources of funding, institutional affiliations and conflicts of interest must be declared in the publication. Reports of research not in accordance with the principles of this Declaration should not be accepted for publication.

Unproven Interventions in Clinical Practice

37. In the treatment of an individual patient, where proven interventions do not exist or other known interventions have been ineffective, the physician, after seeking expert advice, with informed consent from the patient or a legally authorised representative, may use an unproven intervention if in the physician's judgement it offers hope of saving life, re-establishing health or alleviating suffering. This intervention should subsequently be made the object of research, designed to evaluate its safety and efficacy. In all cases, new information must be recorded and, where appropriate, made publicly available.

13. LIST OF TABLES/GRAPHS/LISTINGS	11
13.1 List of Statistical Tables	11
13.2 List of Graphs.....	11
13.3 List of Derived Data Listings	11
14. VERSION HISTORY.....	12

 Confidential

1. List of Abbreviations and Definition of Terms

Abbreviation	Term
AE	Adverse Event
ATC	Anatomical Therapeutic Chemical
BP	Blood Pressure
bpm	Beats per Minute
CA 125	Cancer Antigen 125
CRF	Case Report Form
CT	Computed Tomography
CTCAE	Common Toxicity Criteria for Adverse Events
ECG	Electrocardiogram
ECOG	Eastern Cooperative Oncology Group
ICF	Informed Consent Form
ICH	International Conference on Harmonization
IMP	Investigational Medicinal Product
MedDRA	Medical Dictionary for Regulatory Activities
NCI	National Cancer Institute
RECIST	Response Evaluation Criteria In Solid Tumors
SAE	Serious Adverse Event
SAP	Statistical Analysis Plan
WHO	World Health Organization

 Confidential

2. Introduction

This Statistical Analysis Plan was written for the clinical trial GCT1015-03 conducted in Europe and the United States of America. The ICH guideline E3 "Structure and Content of Clinical Study Reports" was used as a guide to the writing of the plan.

3. Trial Design and Objectives

3.1 Trial Objectives

3.1.1 Primary Objective

- To collect long-term safety data from patients with solid tumors who have been treated with tisotumab vedotin and completed any base trial (i.e., GEN701 or GEN702).

3.1.2 Secondary Objective

- To further evaluate the anti-tumor activity of tisotumab vedotin.

3.2 Trial Design

The trial design is available in section 8.1 Overall Trial Design and Plan of the protocol final version 5.0 dd. 24 September 2018.

3.3 Sample Size Justification

Since the trial will include all patients willing to continue on treatment after completing other tisotumab vedotin trials (i.e., GEN701 and GEN702), no sample size determination can be made. It is expected that approximately 25 patients will enter the GCT1015-03 trial.

4. General Analysis Definitions

Data will be analyzed using SAS (Version 9.4 or higher).

[figure not shown]
Given the low expected number of patients and the heterogeneity between patients at entering this trial with regards to dosing regimen (as followed by the patient in the base trial), indication and response to treatment in the base trial, no formal statistical analyses are planned. Instead, all endpoints will only be listed. All enrolled patients will be included in the listings.

All data collected in this maintenance trial will be listed by base trial, dosing regimen (as followed by the patient in the base trial), indication, patient number and visit (if applicable). All listings will include the first IMP administration date in this trial and the last IMP administration date at the time of the database snapshot or database lock. Whenever applicable the reason for not done will be included in the listings.

When presenting coded data (e.g. medical history, concomitant medication, adverse events), the dictionary and the version used will be mentioned in the footnote. The current version of each dictionary will be used.

In case there will be a need for summary tables, these can be performed using descriptive statistics as follows:

- Categorical data will be summarized in contingency tables presenting frequencies and percentages.

 Confidential

- Continuous data will be summarized using number of non-missing values (n), mean, standard deviation, median, 25th and 75th percentiles, minimum and maximum values.

The following data will be included from the base trials as specified in the respective sections below:

- Medical history data
- Local tumor assessments
- Exposure data

4.1 Trial Period and Visit Window Definitions

4.1.1 Trial Periods

Treatment period will be defined as the period between the date of first IMP administration in the base trial and the date of last IMP administration + 30 days or the date of the end of trial visit in this trial when available.

Trial periods will not be used in the analysis as the data is listed only.

4.1.2 Visit Windows

Visits will be reported as captured in the eCRF.

4.2 Planned Analyses

As this trial may be ongoing for a very long time, potentially several interim analyses may become relevant. Given that it is an open-label trial with no formal hypotheses, this will not require any formal methods such as control of the alpha level. It will simply consist of lists of what has been observed so far with tisotumab vedotin during the trial conduct.

4.3 Definition of Populations (Analysis Sets)

4.3.1 Enrolled Population

The Enrolled Population consists of all patients who sign the informed consent form (ICF).

4.4 Subgroup Definitions

Not defined at the time of final SAP given the objectives and the size of the trial.

4.5 Treatment Assignment and Treatment Arms

Tisotumab vedotin will be administered as an intravenous infusion on Day 1 of each 21-day cycle (once every three weeks [1Q3W]).

The dose will be 2.0 mg/kg or if dose reduced in the base trial continue the same dose. Dose reductions are allowed according to the protocol section 9.5.

4.6 Calculated Variables

Baseline is defined as the last assessment value before or on the date of the first IMP administration in this trial unless specified otherwise.

Confidential

Date/time of first study treatment in the listings refers to first IMP administration in the base trial.

Study days for visit date, assessment date, date of progression and date of death are calculated versus the start of IMP administration in the base trial.

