8.2 Schedule of Activities

Table 1: Trial Flow Chart - 1Q3W Treatment Scheme

Procedure	Screening (up to 21 days before Day 1)	Treatment Period Cycle 1 – X (21-day cycle \pm 7 days) Day 1	End-of-Trial Visit (30 days after last dose + 1 week)	Comments
Informed consent	X			
Eligibility criteria	X			
Demography	X			
Height	X			
Weight	X	X		To be taken at screening and at start of each treatment cycle
Pregnancy test	X	X		To be taken at screening and at start of each treatment cycle for women of childbearing potential
Vital signs	X	X		Blood pressure pulse, heart rate and temperature taken at screening and before and after treatment
ECG	X	X		To be taken at screening and before each treatment
ECOG performance status	X			
Neuropathy assessment	X			
Skin assessment	X			
Ophthalmology evaluation	X	X	X	To be performed according to the schedule in the base protocol. Patients experiencing ocular symptoms must be referred to an ophthalmologist for prompt review (preferably within 72 hours and no later than within 1 week).
Laboratory sampling	X	X	X	Local laboratories will be used. Screening laboratory samples do not need to be repeated if performed at the base trial. Details on laboratory samples are provided in Section 10.3.4.

Procedure	Screening (up to 21 days before Day 1)	Treatment Period Cycle 1 – X (21-day cycle \pm 7 days) Day 1	End-of-Trial Visit (30 days after last dose + 1 week)	Comments
Trial drug administration		X		Treatment administration schedule to follow the treatment schedule in the base protocol.
Preventive eye therapy		X		Preventive eye therapy to be administered in relation to infusions as detailed in Section 9.5.4.
Response assessment (CT-scan, PSA, CA 125)	X	X	X	Last CT-scan of base trial to be used at screening if less than 4 weeks old, otherwise a new CT-scan needs to be obtained. Then, to be performed every 6 weeks (at the end of every second cycle) during Treatment Period, and response to be confirmed 4 weeks later. Response assessments will be recorded in the eCRF. PSA will be performed for CRPC patients. CA 125 will be performed for patients with ovarian cancer.
Radionuclide bone scan		X		For patients with CRPC, assessment of bone metastases by radionuclide bone scan every 12 weeks is recommended, but frequency should be based on local standards. If there is suspicion of progression, another bone scan will be performed twelve weeks later.
AE/SAE review	X	X	X	
Concomitant medication	X	X	X	

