10.3.2 Vital Signs

Vital signs including temperature, blood pressure and heart rate should be recorded at each visit. Within each visit, preferably the same equipment shall be used for vital signs measurements. Vital signs should be assessed just before and no longer than 30 minutes before infusion start, and within 30 minutes after the infusions.

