11.6.4 Information about Infusion-Related Reactions

Information on whether AEs are infusion-related or not must be reported in the eCRF.

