10.1 Anti-tumor Activity

Anti-tumor activity measured by tumor shrinkage (based on sum of the diameter(s) of all target lesions from the CT or MRI scan evaluations) will be listed. Details of target lesions (method, lesion location and specification, description, longest and shortest diameter), non-target lesions (method, lesion location and specification, description, lesion status and specification) and new lesions (method, lesion site and specification and description) will be included. Response assessments including the target lesion overall response, non-target lesion overall response, new lesion status, overall response and date of disease progression will be listed in a separate listing. Disease response or progression should be evaluated according to the current published RECIST (Response Evaluation Criteria In Solid Tumors) version 1.1 (Eisenhauer et al., 2009¹). Baseline will be defined as the last assessment before the first IMP administration in the base trial. Local tumor assessment information available from the base trials will be included in these listings.

 Confidential

Results obtained from an independent, central imaging review will be included when available.

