11.7 Vital Signs and ECG

ECG measurements will be listed including the evaluation (Normal/Abnormal, not clinically significant/Abnormal, clinically significant).

All vital signs results will be listed including a flag for clinically notable values for each of the following parameters:

Clinically notable elevated values

- Systolic BP: ≥ 180 mmHg and an increase ≥ 20 mmHg from baseline
- Diastolic BP: ≥ 105 mmHg and an increase ≥ 15 mmHg from baseline.
- Weight: Increase from baseline of 10%
- Heart rate: ≥ 120 bpm with increase from baseline of ≥ 15 bpm
- Temperature: > 38 °C

Clinically notable below normal values

- Systolic BP: ≤ 90 mmHg and a decrease ≥ 20 mmHg from baseline
- Diastolic BP: ≤ 50 mmHg and a decrease ≥ 15 mmHg from baseline
- Weight: decrease from baseline of $\geq 10\%$
- Heart rate: ≤ 50 bpm with decrease from baseline of ≥ 15 bpm
- Temperature: < 35 °C

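### The date-only baseline in SAP 4.6, read literally, makes the Cycle 1 Day 1 post-infusion vital signs their own baseline, so six blood-pressure and heart-rate flags cannot fire on that record

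*SAP*

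**What the plan says.** The general baseline rule is in SAP 4.6: "Baseline is defined as the last assessment value before or on the date of the first IMP administration in this trial unless specified otherwise". It names a date and gives no clock time or pre-dose condition.

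Protocol 10.3.2 sets the timing on dosing days: "Vital signs should be assessed just before and no longer than 30 minutes before infusion start, and within 30 minutes after the infusions". The comment in Table 1 (Protocol 8.2) agrees: "Blood pressure pulse, heart rate and temperature taken at screening and before and after treatment".

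SAP 11.7 says how the values are used: "All vital signs results will be listed including a flag for clinically notable values for each of the following parameters". A typical criterion is "Systolic BP: ≤ 90 mmHg and a decrease ≥ 20 mmHg from baseline". SAP 11.7 defines no baseline of its own.

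The SAP departs from its general rule in two places, and neither covers vital signs. For tumor assessments, SAP 10.1 says "Baseline will be defined as the last assessment before the first IMP administration in the base trial". For CA 125, SAP 10.2 takes baseline from the initial trial.

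**The concern.** A baseline for a safety flag should precede the exposure whose effect the flag is meant to show. Here the date rule admits a reading taken after the infusion and, because it asks for the last value, prefers it. There are three consequences.

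- The scheduled Cycle 1 Day 1 post-infusion record is compared with itself, so no flag that requires a change can fire on it.
- Every later visit is compared with a post-infusion value.
- The Cycle 1 pre-infusion reading can be flagged as a fall or rise from a value taken after it.

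A blank flag tells the reader of the listing that a value is not notable. At the first infusion in this trial, the blank would carry no information for blood pressure and heart rate. If the vital-sign record holds neither a clock time nor a before/after label, the rule does not settle which same-day value is baseline.

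**Working it through.** **Which flags are affected.** SAP 11.7 lists five parameters, each with a high and a low criterion, so 10 flags. The 2 temperature flags use no baseline. The 2 weight flags do, but no post-infusion weight is scheduled. That leaves 10 − 2 − 2 = 6: systolic, diastolic and heart rate, high and low.

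**Why they cannot fire.** If the post-infusion value *v* is itself the baseline, the change is *v* − *v* = 0. The six flags need a change of at least 20 (systolic) or 15 (diastolic, heart rate). As a check, each flag was evaluated at every integer from 20 to 300: with the record as its own baseline, each fired for 0 of 281 values. With a pre-infusion baseline all six can fire.

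**Examples (assumed readings).**

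| Record judged | Readings | Literal SAP 4.6 | Pre-infusion baseline |
|---|---|---|---|
| Cycle 1 post-infusion systolic | pre 130, post 85 | change 0, no flag | fall of 45 and ≤ 90, flag |
| Cycle 2 systolic of 185 | Cycle 1 pre 150, post 170 | rise of 15, no flag | rise of 35, flag |
| Cycle 1 pre-infusion systolic | pre 90, post 115 | fall of 25 and ≤ 90, flag | change 0, no flag |

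**How often it could matter.** The documents give no blood-pressure distribution or reaction rate, so this is an illustration for the low-systolic flag only. Assumptions: each patient's true level is normal with mean 125 and SD 15 mmHg; each reading adds normal error with SD 9; a share *p* of patients drops by *d* mmHg after the infusion. The flag fires if post ≤ 90 and pre − post ≥ 20.

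Let r(d) be the chance of a flag for a drop of *d*. Under these assumptions r(0) = 0.51%, r(20) = 13.8% and r(40) = 59.4%. The overall rate is (1 − p) × r(0) + p × r(d). For example, with p = 10% and d = 40: 0.9 × 0.51% + 0.1 × 59.4% = 6.4%. The SAP expects about 25 patients ("It is expected that approximately 25 patients will enter the GCT1015-03 trial").

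| Share reacting | Drop (mmHg) | Should be flagged | × 25 patients | Literal SAP 4.6 |
|---|---|---|---|---|
| none | – | 0.5% | 0.1 | 0% |
| 1% | 40 | 1.1% | 0.3 | 0% |
| 2% | 40 | 1.7% | 0.4 | 0% |
| 5% | 20 | 1.2% | 0.3 | 0% |
| 10% | 20 | 1.8% | 0.5 | 0% |
| 5% | 40 | 3.5% | 0.9 | 0% |
| 10% | 40 | 6.4% | 1.6 | 0% |

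Varying the within-patient SD from 6 to 12 widens the range to 0.06%–6.9%.

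**Reverse flag.** At within-patient SD 9, 0.46% to 0.51% of patients would have the Cycle 1 pre-infusion systolic reading wrongly flagged low. With SD 6 to 12 this runs from about 0.06% to 1.4%.

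**Later visits.** At one later visit with no further reactions, in the 10%/40 mmHg scenario, the low-systolic flag rate is 0.51% with a pre-infusion baseline and 0.46% with the literal one. The difference is 0.05 percentage points, or 0.0005 × 25 = about 0.01 patient per visit.

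**The case against.** The strongest reply is that nothing planned depends on these flags. The trial is listings-only, with no tables or graphs planned (SAP 13.1, 13.2). The primary endpoint is adverse events. The flag is one marker in Listing 16.02.03.13, where a 130 and an 85 for the same patient and visit would both appear. Infusion-related events have their own route: "Information on whether AEs are infusion-related or not must be reported in the eCRF", and SAP 11.2 carries the relationship to infusion into the adverse-event listing. Every patient had already received the drug in a base trial. All of this stands, and it caps the point at minor.

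Second, the zero change is conditional. It needs the post-infusion set to be taken, to fall on the infusion date and to be the last set that day. A programmer with a before/after label might also choose the pre-dose value. The condition is fair, but it is what the protocol schedules, and a programmer who did so would be departing from the rule as written.

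Third, the rates rest wholly on assumptions, and the top figure needs 10% of patients to fall by 40 mmHg. That is right, and the table is only an illustration. The inability of the six flags to fire needs no rate assumption. The effect on later visits is negligible on these figures.

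Fourth, the SAP 10.1 wording is tied to the base trial and to scans, so it cannot be carried over unchanged. True: it shows only that the SAP uses a strict before-dose rule elsewhere.

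**Conclusion.** The point holds as a minor error. SAP 4.6 read literally, with the protocol's own vital-sign schedule, disables six of the ten notable-value flags on the scheduled Cycle 1 Day 1 post-infusion record. That follows from the text, given a post-infusion set taken on the infusion date and last that day. In patients, the size is uncertain but small: on the stated assumptions, between 0.1 and 1.6 of about 25 would miss a low-systolic flag; the other five flags were not simulated. No endpoint changes, and no raw value is hidden.

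**What to change.** Add one sentence to SAP 4.6 or 11.7:

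> *For vital signs, baseline is the last non-missing value before the start of the first IMP infusion in this trial. On Cycle 1 Day 1 the pre-infusion record is used, identified by its before/after-infusion label, or by clock time if recorded.*

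The cost is that sentence and one programming condition. It needs a before/after label or a clock time on the vital-sign record. SAP 11.1 confirms start and end times for the infusion only, so the sponsor should check which of the two the eCRF holds. No trial procedure changes.
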